11.4 Quality Control of Collected Data – 11.11 Handling and Transmission of Data

All appropriate sections of the case report form (CRF): (See appendix) will be completed by the coordinator, viewed and signed by the principal investigator and entered into the database within two weeks following the subject's discharge for the index procedure. The follow-up forms will be completed within a timely fashion after follow-up.

Study monitors designated by the sponsor will review the information documented in the CRF to verify that the recorded information is consistent with the medical record or other source documents and that input of this information into the data base is accurate. Errors or incomplete data will be rectified. All information will be treated as confidential. The following individuals will have full access to the data: Principal investigator, clinical

coordinator, statistician Co-investigators, vascular technicians, Core Lab personnel and study monitors will have access on an as needed basis.

Table 2. Adverse Event Definitions and Categorizations

Adverse Event	Any undesirable medical occurrences in a subject whether or not it is related to the study device, procedure or study requirements that is identified or worsens during the clinical study	
Major Adverse Event	A primary safety endpoint adverse event defined as Szilagyi Grade III infection of the randomized incision and all-cause mortality	Grade III Szilagyi infection of the randomized incision All-cause mortality
Serious Adverse Event	Any adverse event that results in death, is life threatening, requires > 24 hour in-patient hospitalization, or prolongation of an existing hospitalization, requires intervention to prevent permanent impairment/damage or results in persistent or significant disability/incapacity	Myocardial Infarction Congestive Heart Failure Pulmonary Embolus Respiratory Failure Stroke Cardio/Pulmonary Arrest Thirty day hospital readmission for Grade II or III Szilagyi infection of the randomized incision
Unanticipated Adverse Event	Any serious adverse event leading to injury, illness or death of a subject not previously identified in nature, severity or degree of incidence in this protocol, literature or application (including a supplementary plan or application) that may be directly related to use of the device	

Table 3. Procedure Related Categories for Adverse Events

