Procedure Related Adverse Event	AE that have a strong temporal relationship to the procedure and an alternative etiology is unlikely
Probably Procedure Related Adverse Event	AE that have a strong temporal relationship to the procedure and an alternative etiology is less likely than the potential relationship to the procedure
Probably–Not Procedure Related Adverse Event	AE that have minimal or no temporal relationship to the procedure and/or a more than likely alternative etiology
Not Procedure –Related Adverse Event	AE is due to the underlying disease state or concomitant medication or therapy and not caused by the procedure

Criteria for MAE and SAE

Serious Infection-	Grade III Sziglgyi infection of the randomized incision
Myocardial Infarction-	Per the ESC/ACC definition for acute, evolving or recent MI Typical rise and gradual fall of Troponin or more rapid rise and fall of (CK-MB) biomarkers or myocardial necrosis with at least one of the following: 
 • Ischemic symptoms • Development of pathologic Q wave on ECG • ECG changes indicative of ischemia (ST segment elevation or depression) or coronary artery intervention (ie: coronary angioplasty • Pathologic findings of an acute MI
Congestive Heart Failure-	New or worsening shortness of breath confirmed by chest x-ray findings consistent with CHF and/or requiring unscheduled dialysis or fluid restriction
Cerebrovascular Accident-	A neurologic deficit lasting more than 24 hours, or lasting less than 24 hours with a brain imaging study showing infarction.
Pulmonary Embolus-	Embolus in the pulmonary vascular documented by CT findings
Respiratory Failure-	Respiratory difficult requiring intubation
Cardio-Pulmonary Arrest-	Loss of pulse and respiration. Need for cardio-pulmonary resuscitation to prevent impending death

Interim analysis will be performed of the primary and secondary endpoints after half of the subjects are enrolled and again when all subjects are enrolled. Anova will be used to determine differences in infection rates between the two treatment arms. The PI will verbally communicate the findings to Acelyty with recommendations to continue, stop the study or make changes to the protocol if additional patients are needed to achieve statistical significance. These will be provided in writing within 4 weeks.

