13.0 Withdrawal of Subjects

13.1 Circumstances under which subjects would be withdrawn without their consent

All study subjects have the right to withdraw their consent at any time during the study. However, withdrawal of a subject from the study can occur at the direction of the PI or the sponsor. Reasons for physician directed withdrawal could include but are not limited to: the subject's not adhering to the study follow-up protocol, the subject enrolls in another study which conflicts with this study's primary or secondary endpoints, or if the physician deems it is in the patients best interest for safety or welfare of the subject to withdraw.

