20.3 Time necessary to conduct the research project

The projected completion time for the study is 18-24 months allowing a minimum recruitment period of 12 months with an additional 6-9 months if necessary and 3-6 months for data analysis, write-up and study closure.

Anticipated Personnel time requirements

- 1/4 FTE Study Consultant for development of protocol and case report forms, statistical analysis, preparation of manuscript and slide presentation
- 1/2 FTE clinical coordinator for project oversight
- 1 FTE research assistant for start-up, patient screening, data collection, entering of data and maintenance of the data base, study closure
- 10-20 hours Bio-statistical consultation

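### By-arm interim results go through the PI to the device maker at half enrolment, with no firewall, so the trend can affect how later outcomes are recorded or retained and whether the trial is extended.

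*Combined protocol and SAP*

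**What the plan says.** The interim paragraph closes the section 11.4–11.11 text, just before section 13.0. It says "Interim analysis will be performed of the primary and secondary endpoints after half of the subjects are enrolled", with a second analysis at full enrolment, and "Anova will be used to determine differences in infection rates between the two treatment arms". On disclosure: "The PI will verbally communicate the findings to Acelyty with recommendations to continue, stop the study", or to "make changes to the protocol if additional patients are needed to achieve statistical significance". Of the report it adds "These will be provided in writing within 4 weeks". The title page and section 1.1a show that the recipient is both the sponsor and the maker of Prevena.

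The same parties have roles in outcome data and retention:

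- **CRFs.** Section 11.4 says the forms "will be completed by the coordinator, viewed and signed by the principal investigator". The definition of the PI in section 32.0 adds that this signature attests to accuracy and completeness.
- **Data access.** Section 11.4–11.11 gives the PI, the coordinator and the statistician full access. Sponsor-designated monitors check the CRFs and the database entries.
- **Withdrawal.** Section 13.1 says "withdrawal of a subject from the study can occur at the direction of the PI or the sponsor". Its list of reasons for physician-directed withdrawal is expressly not exhaustive, and no separate reasons are given for the sponsor.
- **Statistical resource.** Section 20.3 lists "10-20 hours Bio-statistical consultation".

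The text supplied describes no monitoring committee, no restriction on who sees interim results, no blinded wound assessor and no pause in enrolment. Section 9.2 points to a section 12.0 on data safety monitoring, but that heading does not appear, so these absences can be stated only for the text supplied.

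**The concern.** Interim comparisons by arm are normally kept from those who run the trial and from a sponsor with an interest in the result, because people who know the trend can act on it, even unintentionally. Here the disclosure is a stated rule, not an omission, and what is passed on is the findings themselves as well as a recommendation.

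Three things are at stake in the second half:

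- **Recording.** The primary endpoint is the Szilagyi grade. The step from none to grade I (dermis only) is a matter of judgement, made with the treatment visible.
- **Retention.** A directed withdrawal before day 30 can lose an outcome.
- **Extension.** The decision to add patients would be taken by parties holding the by-arm result, with significance as its stated aim.

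This is separate from repeated testing. A corrected alpha boundary would not remove it.

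**Working it through.** **Inputs.** Section 9.13 gives 70 per arm, type I error 0.05, and grade probabilities (none, I, II, III) of (0.90, 0.08, 0.019, 0.001) for Prevena and (0.70, 0.16, 0.11, 0.03) for Dermabond. The first look is at half enrolment, so 35 + 35.

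**1. The plan's own figure.** Simulating the two vectors with 70 per arm and a two-sided proportional-odds score test gives power 0.887, against the stated 0.88. It reproduces.

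**2. What the first look would reveal.** Expected infections are 35 × 0.10 = 3.5 on Prevena and 35 × 0.30 = 10.5 on Dermabond, 14 in all. This assumes complete 30-day outcomes. The look is triggered by enrolment, so fewer may be available. With complete outcomes and the planning rates, the chance of p < 0.05 at 35 + 35 is about 60% (score test; the plan names ANOVA for this look). The disclosed result would often be a clear signal.

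**3. Illustration of misrecording.** Assumption, not in the documents: no true difference, and half of second-half grade I infections in one arm recorded as none. The second half is half the arm, so 0.5 × 0.5 = 0.25 of that arm's grade I infections are affected.

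| Grade vector in both arms | True rate | Recorded rate in affected arm | Apparent odds ratio |
|---|---|---|---|
| Dermabond planning | 0.30 | 0.30 − 0.25 × 0.16 = 0.26 | (0.30/0.70)/(0.26/0.74) = 1.22 |
| Average of the two | 0.20 | 0.20 − 0.25 × 0.12 = 0.17 | (0.20/0.80)/(0.17/0.83) = 1.22 |
| Prevena planning | 0.10 | 0.10 − 0.25 × 0.08 = 0.08 | (0.10/0.90)/(0.08/0.92) = 1.28 |

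Simulated two-sided rejection is about 0.07 in each case, against about 0.05 with no misrecording.

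**4. Sensitivity to the assumed fraction.** Here a fraction m of all second-half Prevena infections is recorded as none, again with no true difference, using a two-sided test of infected versus not:

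| Infection rate, both arms | m = 0 | m = 0.1 | m = 0.3 | m = 0.5 |
|---|---|---|---|---|
| 10% | 0.051 | 0.052 | 0.060 | 0.083 |
| 20% | 0.050 | 0.053 | 0.073 | 0.119 |
| 30% | 0.052 | 0.056 | 0.092 | 0.172 |

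At a 20% rate, false findings favouring Prevena rise from 2.5% (m = 0) to 6.5% (m = 0.3) and 11.6% (m = 0.5). Small fractions do little and large ones matter. The documents give no basis for choosing among them.

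**The case against.** The strongest reply is that the trial is open-label. Anyone inclined to grade by product can do so from the first patient, and surgeons will form impressions without an interim report. That stands: interim knowledge only adds to a bias already possible, and nothing in the documents separates the two. A formal by-arm result is still different from an impression, and the plan can avoid sharing it.

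A reader might infer more than the text supports:

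- **That the PI grades the wounds.** No section says so. The coordinator completes the forms and the PI reviews and signs. The sponsor's monitors also compare CRFs with source records, which is some protection, although they act for a party that would know the trend.
- **That changing who is approached biases the comparison.** Allocation is 1:1, stratified, in random blocks of 4 or 8 (section 9.11). A shift in who is approached affects both arms and does not by itself bias the contrast.
- **That withdrawal removes patients from the analysis.** The primary analysis is intention to treat (section 9.12), and section 8.1 follows all randomised patients to 30 days. The risk is narrower: outcomes can still be lost, and section 25.1 foresees withdrawal with missing data censored.
- **That the report is only oral.** A written version follows within 4 weeks.
- **That both looks carry this risk equally.** Only the first precedes planned enrolment. The second matters in this way only if patients are added.

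**Conclusion.** The point holds as a credible and avoidable risk, not as a demonstrated bias. The plan routes by-arm results through the PI to the device maker with half the patients still to enrol. Both have a role in checking the record or in retention, and both would take part in a result-driven decision to extend. That the PI sees the results by arm follows from the PI reporting the findings and having full data access; the plan does not say who runs the ANOVA.

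The size is unknown. The odds ratio of about 1.22 to 1.28 and rejection of about 0.07 against 0.05 rest on an assumed one-sided misrecording of half of second-half grade I infections. A reader might take 0.07 as the trial's actual error rate. The documents do not support that, because neither the fraction nor its direction can be derived from them. The change is worth making because it is simple and needs no new board.

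**What to change.** Three linked edits are needed. Changing the interim paragraph alone would leave the PI and coordinator free to tabulate results by arm.

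1. **Interim paragraph.** State that the study statistician runs the interim analysis under a rule written in advance and sends the PI, IRB and sponsor only a written recommendation. No by-arm results go to the PI, surgeons, coordinator or sponsor before the final analysis. Remove the verbal report of findings.
2. **Data access in section 11.4–11.11.** Replace the full access of the PI and coordinator with wording under which they and the sponsor's monitors may check individual records but may not tabulate outcomes by arm before the final analysis.
3. **Adding patients.** Either delete the option to add patients in pursuit of significance, or replace it with a rule fixed in advance and applied by the statistician.

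**Cost.** This is a protocol amendment with no change in sample size. The PI and sponsor lose early sight of trends and the free option to extend on seen results. Some of the 10–20 biostatistical hours in section 20.3 go to the interim analysis. No interim task is assigned to those hours now, and section 20.3 places statistical analysis with the study consultant, so the allocation should be confirmed. The open-label grading bias present from the start remains.

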7.2 Duration of enrollment period

The expected enrollment phase is 12 months

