7.3 Projected completion date

The anticipated completion date for the study enrollment, follow-up data analysis, report preparation is 05/31/17.

Figure1. Study flow Diagram from Subject Screening to Follow-up

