9.0 Procedures Involved

9.1 Study Design

This is a prospective multicenter randomized double arm study to evaluate the prevention of groin wound infections in patients undergoing vascular surgery which requires ≥ 8 cm groin incision.

9.11 Randomization Plan:

We will employ a 1:1 randomization to either Prevena or Dermabond using a stratified blocked randomization plan with strata determined as a single incision or a bilateral incision with sequences of random block sizes of 4 or 8. Within the bilateral incision strata, one incision will be randomly chosen relative to defining a single endpoint measure, with site of incision essentially serving as a secondary substratum.

9.12 Statistical Analysis Plan Outline:

Primary Endpoint

The primary endpoint for this trial will be Szilagyi wound infection grade quantified on an ordinal scale (none, grade I: infection contained to the dermus, grade II: infection extending into the subcutaneous tissue but the arterial graft is not involved, grade III: infection of the arterial graft or native vessel underlying the incision). The primary analysis will be intent to treat and carried forth using an ordinal regression model with a stratified likelihood accounting for the primary randomization strata (incision number) and binary indicator variable for treatment arm with the primary test of treatment efficacy being the proportional odds different from 1. In the event of sparse data at the higher grades of infection (<2% at grade III), categories II and III will be combined. For the bilateral incision strata, the primary endpoint will be determined by randomly choosing a single incision as determined within the randomization scheme.

Secondary Endpoint

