The secondary endpoint will be a comparison of cost of treatment between the two arms and will be considered an exploratory analysis. We will utilize regression approaches to account for potential selection bias and censored cost endpoints. We have completed a preliminary appraisal of the additional per patient hospital costs (dispersed over the entire sample) for treating groin wound infections using the following assumptions. The associated wound infection rate for Prevena would be 6%.³ Groin wound infections for Prevena and Dermabond would require comparable care. Although lower wound severity grades have been reported for Prevena³ which could potentially decrease the complexity, duration and cost of subsequent treatment of wound infection for this group, the finding was not statistically significant.³ Therefore, we projected that treatment of groin wound infection in both groups would include an increased 10 day hospital length of stay,¹ seven days of IV antibiotics, daily CBC with or without differential and 2 cultures. We have estimated that the additional per patient cost of treating groin wounds if Prevena were used preemptively (\$935- \$1,114) would be similar to Dermabond (\$869- \$1,168) if the incidence of wound infection with Dermabond is $\leq 10\%$.

9.13 Sample size rationale:

Given $N=140=70+70$ total subjects and setting the Type I error rate = 0.05, we will have the power of 0.88 to detect a proportional odds of 4.9 different from 1. For our calculations, we assumed a probability vector for the ordinal scale (none, grade I, grade II, grade III) of (0.90, 0.08, 0.019, 0.001) for the Prevena treatment arm and (0.70, 0.16, 0.11, 0.03) for the Dermabond arm respectively. The power estimate was carried forth using 10,000 Monte Carlo simulations. This volume should be easily attainable over a 12 month period because on average 484 lower extremity revascularizations and 100 Abdominal Aortic Aneurysm Repairs are performed annually at Kaleida Health. While most of these procedures (85%) are completed by endovascular approach, access by groin cutdown is necessary in 25% of EVAR and 10% of EVI in addition to the planned open lower extremity revascularizations, which should allow for adequate numbers. SPSS 22 will be used to perform the statistical analysis.

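### The interim paragraph lets the trial be enlarged because the between-arm result is not yet significant, with no error-control rule, so the stated type I error of 0.05 is not assured.

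*Combined protocol and SAP*

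**What the plan says.** The interim paragraph follows the table of criteria for major and serious adverse events and precedes section 13.0. It sets the timing: "Interim analysis will be performed of the primary and secondary endpoints after half of the subjects are enrolled and again when all subjects are enrolled". It names the test: "Anova will be used to determine differences in infection rates between the two treatment arms". The PI passes the findings to the sponsor verbally, then in writing within 4 weeks, with "recommendations to continue, stop the study or make changes to the protocol if additional patients are needed to achieve statistical significance".

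Sections 9.13 and 11.2 describe a design with one analysis: 70 per arm, "setting the Type I error rate = 0.05", and power 0.88 from 10,000 simulations. Neither mentions interim looks. Sections 9.12 and 11.1 define the primary analysis as a stratified ordinal regression, "with the primary test of treatment efficacy being the proportional odds different from 1".

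The supplied text contains no significance level per look, stopping boundary, statement that a look spends no alpha, cap on sample size or adjusted final test. Section 9.2 refers to a section 12.0 on data safety monitoring, but no heading with that number appears in the supplied text.

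**The concern.** The stated error rate belongs to one test on 140 patients. The interim paragraph describes something else: the arms are compared, the PI sees the result, and one listed response is to add patients because significance has not been reached. Adding patients does not by itself inflate the error. Adding them because the between-arm result at 140 fell short does, since the trial gets a second chance to cross the same threshold. Nothing written compensates for that.

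A positive result reached that way would not carry the 5% false-positive rate that the plan states. If the half-enrolment look could also end the trial for benefit at an unadjusted 0.05, the error would rise further and the reported effect would tend to be too large.

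**Working it through.** **Inputs from the documents.** Looks at 70 and 140 patients (interim paragraph); 1:1 allocation and N = 140 (9.11, 4.1); overall type I error 0.05 and planning probabilities for none, grade I, II and III of 0.90, 0.08, 0.019, 0.001 (Prevena) and 0.70, 0.16, 0.11, 0.03 (Dermabond) (9.13); 30-day visit with a window of 25 to 40 days (7.1, 9.6).

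**Assumptions, because the documents give none.** Two-sided 0.05 (|Z| > 1.96) at every test; one extension of 70, to 210 in total; complete outcomes unless stated.

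**The plan's own figure.** Simulating the two planning vectors with 70 per arm and an unstratified ordinal (Wilcoxon) test at two-sided 0.05 gives power of about 0.887, against the stated 0.88. One-sided 0.05 gives 0.938. The stated power is therefore that of one two-sided test.

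**Method for the error rate.** Under no treatment effect, cumulative statistics at n1 and n2 patients are jointly normal with correlation √(n1/n2). That is √(70/140) = 0.707 for the two planned looks and √(140/210) = 0.816 for 140 followed by 210.

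- Error for two tests = 1 − P(|Z1| ≤ 1.96 and |Z2| ≤ 1.96).
- Error with an extension only when p < q at 140 = 0.05 + P(0.05 ≤ p140 < q and |Z210| > 1.96).

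**Results.**

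| Reading of the paragraph | Type I error |
|---|---|
| No interim claim; no extension, or one decided without arm results | 0.050 |
| No interim claim; extension decided at 70; one final test | 0.047 to 0.058, depending on the rule |
| No interim claim; extension after non-significance at 140, only if p < 0.10 | 0.060 |
| Same, only if p < 0.20 | 0.069 |
| Same, always | 0.077 |
| p < 0.05 at 70 or 140 counts as success; no extension | 0.083 |
| Same, with the three extension rules after 140 | 0.091, 0.099, 0.107 |

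Simulated ordinal data at the pooled planning rates agree: 0.0596, 0.0689 and 0.0767 for the three extension rules without an interim claim.

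**If stopping did mean efficacy.** Under the planning vectors, ANOVA on any infection with 35 per arm crosses 0.05 with probability 0.56. In those trials the mean observed difference in infection rate is 0.26, against a true 0.30 − 0.10 = 0.20.

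**Outcomes pending at each look.** Both looks are triggered by enrolment. Section 7.2 says "The expected enrollment phase is 12 months"; section 20.3 allows a "minimum recruitment period of 12 months with an additional 6-9 months if necessary", so up to 21 months. Number pending = 140 × visit day ÷ recruitment days:

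- day 40, 12 months: 140 × 40 ÷ 365 = 15.3
- day 25, 21 months: 140 × 25 ÷ 639 = 5.5

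So about 5 to 15 outcomes could be missing at each look. If the full-enrolment look were itself a test of success and a separate final test followed, the two-test formula with n1 = 140 − 5 or 140 − 15 and n2 = 140 gives 0.059 or 0.065, with no interim claim and no extension.

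**The case against.** The strongest reply is that the inflation is conditional. The paragraph never says that p < 0.05 at half enrolment counts as success. The synopsis lists groin wound infection as the primary safety endpoint, and the paragraph sits where a data safety monitoring section would be, so stopping may well mean stopping for safety. A reader might infer that the plan tests for efficacy twice at 0.05 and so carries an error of 0.083 or 0.107. The documents do not support that as a statement of what is planned, and those figures hold only if stopping includes an unadjusted efficacy stop. This part of the reply stands. It does not reach the extension clause, whose stated purpose is to attain significance.

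Second, the extension is only a recommendation, and section 31.1 requires written amendments. An amendment could add an error rule, but section 31.1 does not ask for one. An amendment prompted by an unblinded non-significant result does not restore the error rate.

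Third, the full-enrolment look may simply be the final analysis. That is possible, and then it is not an extra test. It would still be triggered before the last patients reach their 30-day visit.

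Fourth, a rule might lie in text that was not supplied, such as the section 12.0 that section 9.2 cites. This cannot be excluded, so the finding is limited to the supplied text.

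The ANOVA wording is a smaller matter of consistency. Counting ANOVA at 140 as well as the ordinal test moves the simulated error only from 0.0823 to 0.0868.

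**Conclusion.** The point holds, and its weight rests on the significance-driven extension. If that clause is used after a non-significant between-arm result at 140, the type I error is 0.060 to 0.077 instead of 0.05, assuming two-sided 0.05 tests and one extension of 70 patients. No efficacy claim at half enrolment is needed for this. If an unadjusted efficacy stop is also allowed, the range is 0.091 to 0.107; with that stop and no extension it is 0.083. An extension decided at 70 with one final test makes little difference (0.047 to 0.058).

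A reader might go further and conclude that the trial's error rate is in fact above 0.05. The documents do not show that. With no interim claim and no unblinded extension it stays at 0.050. What they show is that the plan permits a route above 0.05 and contains nothing to close it, so the clause should be changed before the primary result is interpreted.

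**What to change.** 1. **State what the half-enrolment look is for.** Either say that it cannot support an efficacy claim and keep 0.05 for the final analysis, or pre-specify a group-sequential boundary. For example, two-sided p < 0.005 with 70 outcomes and p < 0.048 with 140 gives an overall error of 0.050. If the look has already taken place, a boundary can no longer be pre-specified; disclose the look and how it was used.
2. **Run one final analysis.** Use the stratified ordinal model of sections 9.12 and 11.1 after all 140 patients complete the 30-day visit, in place of the ANOVA look at full enrolment.
3. **Replace the whole clause on protocol changes.** Deleting only its condition would leave an open licence to change the protocol after seeing arm results. Suggested text: *No change to the sample size or the primary analysis may be based on between-arm results. Any sample size review will use only the pooled infection rate, will be decided by persons (including the PI) who have not seen between-arm results, and will not exceed a stated maximum N.* The PI must therefore not receive the arm comparison while such a review remains possible.

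**Cost.** There is no power loss if the interim makes no efficacy claim. With the boundary above, power under the planning vectors goes from 0.886 to 0.884. The sponsor gives up enlarging the trial on an unblinded non-significant result. The change is wording only if the half-enrolment look is still ahead. Enrolment status is not given, and this version (August 11, 2017) is later than the completion date in section 7.3 ("follow-up data analysis, report preparation is 05/31/17"). If the look has passed, the change is disclosure plus the rule for the final analysis.
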